**4.2 Additional Criteria To Be Met Prior To Study Enrollment**

All patients must fulfil all of the following criteria to be eligible for randomization to the study.

4.2.1 Patients must have solid tumors that demonstrate POLE or POLD1 mutations identified at study entry via plasma cfDNA testing or tumor tissue testing for POLE and POLD1 mutations. A CLIA-certified testing of tumor tissue demonstrating POLE or POLD1 mutation can qualify for eligibility and randomization, however plasma will be submitted for central cfDNA testing. In the event of discordance between tissue and central laboratory testing, the patient will continue in study but will not be included in the primary analysis. These patients will however be included in the secondary analysis.

**4.2.2 Prior Therapy**

- Patients must have recovered to  $\leq$  grade 1 from all reversible toxicity related prior systemic or radiation therapy and have a 2 weeks washout.
- Previous major surgery is permitted provided that it has been at least 28 days prior to patient registration and that wound healing has occurred.

**4.2.3 Laboratory Requirements**

(must be done within 14 days prior to enrollment).

Hematology	White Blood Cells	$\geq 2.0 \times 10^9/L$ (2000/ $\mu$ L)
	Absolute neutrophils	$\geq 1.5 \times 10^9/L$ (1500/ $\mu$ L)
	Platelets	$\geq 100 \times 10^9/L$ ( $100 \times 10^3/\mu$ L)
	Hemoglobin	$\geq 80$ g/L* (8.0 g/dL)
Chemistry	Bilirubin	$\leq 1.5 \times$ ULN (upper limit of normal)**
	AST and/or ALT	$\leq 3 \times$ ULN
	Serum creatinine or: Creatinine clearance***	$\leq 1.5 \times$ ULN $\geq 40$ mL/min
	
* Contact CCTG if hemoglobin is <math>< 80</math> g/L and the patient is not decompensated, is asymptomatic and transfusion is not indicated.
 
** If confirmed Gilbert's, eligible providing <math>\leq 3 \times</math> ULN.
 
*** Creatinine clearance to be measured directly by 24 hour urine sampling or as calculated by Cockcroft and Gault equation below:
 
Females: GFR = <math>1.04 \times (140\text{-age}) \times \text{weight in kg}</math>  <math>\text{serum creatinine in } \mu\text{mol/L}</math>
 
Males: GFR = <math>1.23 \times (140\text{-age}) \times \text{weight in kg}</math>  <math>\text{serum creatinine in } \mu\text{mol/L}</math>
	

4.2.4 Patients must be willing to consent to provision of archival tissue (tumor block or minimum of 20 slides cut at a minimum of 4 micron thickness - fewer slides may be accepted if discussed with CCTG) or fresh biopsy (optional) for correlative analyses and the center/pathologist must have agreed to the submission of the specimen(s). Patients will not be excluded if they have POLE/POLD1 mutations in tumor detected by testing outside of this protocol, and additional archival tissue is not available and/or optional fresh biopsy is not possible.

4.2.5 Patient consent must be appropriately obtained in accordance with applicable local and regulatory requirements. Each patient must sign a consent form prior to enrollment in the trial to document their willingness to participate.

Patients who cannot give informed consent (i.e. mentally incompetent patients, or those physically incapacitated such as comatose patients) are not to be recruited into the study. Patients competent but physically unable to sign the consent form may have the document signed by their nearest relative or legal guardian. Each patient will be provided with a full explanation of the study before consent is requested.

4.2.6 Patients must be willing and able to comply with scheduled visits, treatment schedule, laboratory testing, and other requirements of the trial.

4.2.7 In accordance with CCTG policy, protocol treatment is to begin within 2 working days of patient randomization.

4.2.8 Women of childbearing potential (WOCBP) and men who are sexually active with WOCBP must have agreed to use a highly effective contraceptive method as indicated in Section 9.3. A woman is considered to be of "childbearing potential" if she has had menses at any time in the preceding 12 consecutive months. In addition to routine contraceptive methods, "effective contraception" also includes heterosexual celibacy and surgery intended to prevent pregnancy (or with a side-effect of pregnancy prevention) defined as a hysterectomy, bilateral oophorectomy or bilateral tubal ligation, or vasectomy/vasectomized partner. However, if at any point a previously celibate patient chooses to become heterosexually active during the time period for use of contraceptive measures outlined in the protocol, he/she is responsible for beginning contraceptive measures.

Female patients of childbearing potential who are sexually active with a non sterilized male partner must use at least one highly effective method of contraception (failure rate of < 1% per year) while on study and for 23 weeks after the last dose of nivolumab and or ipilimumab. Male partners of a female patient and non-sterilized male patients who are sexually active with a female partner of childbearing potential must use any contraceptive method with a failure rate of < 1% per year for 31 weeks after the last dose of nivolumab and or ipilimumab. Female partners of a male subject must use a highly effective method of contraception throughout this period. Cessation of birth control after this point should be discussed with a responsible physician. See Section 9.3 for additional details.

WOCBP will have a pregnancy test to determine eligibility as part of the Pre-Study Evaluation (see Section 5.0); this may include an ultrasound to rule-out pregnancy if a false-positive is suspected. For example, when beta-human chorionic gonadotropin is high and partner is vasectomized, it may be associated with tumor production of hCG, as seen with some cancers. Patient will be considered eligible if an ultrasound is negative for pregnancy.

Women must not breastfeed while on study and for 23 weeks after the last dose of nivolumab and/or ipilimumab.

4.3 Exclusion Criteria

Patients who fulfill any of the following criteria are not eligible for admission to the study:

4.3.1 Patients with a history of other untreated malignancies or malignancies, which required therapy within the past 2 years. Patients with a prior or concurrent malignancy whose natural history or treatment does not have the potential to interfere with the safety or efficacy assessment of the investigational regimen may be eligible after consultation with the CCTG.

4.3.2 Patients with primary CNS tumors are not eligible.

4.3.3 Patients with active brain metastases or leptomeningeal metastases are not eligible. Patients with brain metastases are eligible if these have been treated and clinically stable. There must also be no requirement for immunosuppressive doses of systemic corticosteroids ( $> 10$  mg/day prednisone equivalents).

4.3.4 History of primary immunodeficiency, history of allogeneic organ transplant that requires therapeutic immunosuppression and the use of immunosuppressive agents within 14 days of study drug administration\*.

\* *NOTE: Intranasal/inhaled corticosteroids or systemic steroids that do not exceed 10 mg/day of prednisone or equivalent dose of an alternative corticosteroid are permissible in the absence of active autoimmune disease.*

4.3.5 Active or prior documented autoimmune or inflammatory disorders. Including, inflammatory bowel disease (e.g. colitis or Crohn's disease), diverticulitis with the exception of diverticulosis, celiac disease or other serious gastrointestinal chronic conditions associated with diarrhea), systemic lupus erythematosus, Sarcoidosis syndrome, or Wegener syndrome (granulomatosis with polyangiitis), rheumatoid arthritis, hypophysitis, uveitis, etc., within the past 3 years prior to the start of treatment.

Patients with vitiligo, type I diabetes mellitus, residual hypothyroidism due to autoimmune condition only requiring hormone replacement, psoriasis not requiring systemic treatment, or conditions considered to be of low risk for recurrence are permitted to enroll.

4.3.6 History of hypersensitivity to nivolumab or ipilimumab or any excipient.

4.3.7 Any previous treatment with a PD-1 or anti-PD-L1, anti-PD-L2 inhibitor, including nivolumab or an anti-CTLA4, including ipilimumab, or drug specifically targeting T-cell stimulation or immune checkpoint pathways.

4.3.8 Patients with serious illnesses or medical conditions which would not permit the patient to be managed according to the protocol (including corticosteroid administration), or would put the patient at risk. This includes but is not limited to:

- History of significant neurologic or psychiatric disorder which would impair the ability to obtain consent or limit compliance with study requirements.

- Active infection requiring systemic therapy; (including any patient known to have active hepatitis B, hepatitis C or human immunodeficiency virus (HIV) or tuberculosis or any infection requiring systemic therapy).
- Active peptic ulcer disease or gastritis.
- Active pneumonitis.

4.3.9 Patients receiving concurrent treatment with other anti-cancer therapy or other investigational anti-cancer agents.

4.3.10 Patients who have experienced untreated and/or uncontrolled cardiovascular conditions and/or have symptomatic cardiac dysfunction (unstable angina, congestive heart failure, myocardial infarction within the previous year or cardiac ventricular arrhythmias requiring medication, history of 2nd or 3rd degree atrioventricular conduction defects).

4.3.11 Pregnant or lactating women.

4.3.12 Men who are sexually active with women of childbearing potential and women of childbearing potential must agree to use adequate contraception as described in Section 4.2.8.

## 5.0 PATIENT EVALUATION FLOWSHEET: PRE-TREATMENT, ON STUDY, AND AFTER TREATMENT

All patients entered on study must be evaluated according to the schedule outlined below with documentation submitted according to the schedule in Appendix IV.

Required Investigations	Prior to Screening	Prior to Enrollment (Day -14 to -1)	Cycle 1 and all cycles beyond (Cycle = 6 weeks)			At disease progression	4 weeks after completion of protocol therapy	Q3 month follow-up
			Day 1 each cycle	Cycle 1, Day 15 Only	Cycle 1, Day 29 Only			
History and Physical Exam								
Including: height, weight, ECOG performance status, documentation of all measurable and non-measurable disease, clinical tumor measurements (if applicable)	ECOG only within 28 days	X	X	X	X		X	
Blood pressure, heart rate, temperature (after baseline to be taken as per institutional standard of care prior to, during and after study drug administration)		X						
Laboratory Procedures/Assessments								
CBC's with differential	X 	X	X	X	X		X	X 
Serum creatinine, electrolytes (calcium, magnesium, sodium, potassium, chloride), LDH, AST and/or ALT, bilirubin, ALP, glucose, amylase  , lipase  , TSH  , BUN or serum urea level	X 	X	X	X	X		X	X 
PTT, PT/INR		X	As clinically indicated					
Hep B/C (HBV, sAG, HCV antibody)		X						
Pregnancy Test 		X						
Tumor Markers 		X	X				X 	
Radiology								
Tumor Imaging (Chest, abdomen, and pelvis; other scans as necessary to document disease) 		within 28 days prior to randomization or 35 if negative	Every 12 weeks ± 1 week 				X 	X 
MRI brain (if clinically indicated)		within 28 days prior to randomization or 35 if negative				X		
Other Investigations								
EKG (if clinically indicated)		X						
Adverse events		X	Continuously		X	X		X 
Survival status								X
Correlative Studies								
Tissue (archival tissue at baseline; optional biopsy at PD)		X				X 		
Correlative Blood 	X	X	X 	X (cycle 1 only)		X 		

Footnotes are on next page ...

- 1 Bloodwork Timing: Pre-treatment blood draws may be done the day prior to treatment if necessary, and when treatment is to begin on a Monday, may be done on the previous Friday (maximum 72 hours prior to treatment). In order to ensure that nadir counts are not missed, every effort should be made to do interim blood draws within 24 hours of the day specified in the protocol.
- 2 Confirmation that the patient would meet the requirements for randomization (CBC with differential, serum creatinine, bilirubin, and AST&/or ALT only). These lab results may be ascertained based on patient chart review. It is not necessary to repeat these labs prior to the screening step for the purposes of this study, if results already available within the previous 28 days.
- 3 It is preferable that both amylase and lipase are assessed. For sites where only 1 of these parameters is routinely measured then either lipase or amylase is acceptable.
- 4 Free T3 and free T4 will be measured if TSH is abnormal.
- 5 To be done additionally every 3 months thereafter to follow abnormal lab results felt related until resolved to  $\leq$  Grade 2.
- 6 Women of child-bearing potential only (urine or serum test). Must be performed within 72 hours prior to administration of study drug. To be done every 4 weeks when on-study.
- 7 Tumor markers including CEA, CA-125, CA-19-9, etc., as indicated per standard of care testing for primary tumor. If elevated at baseline, will be monitor serially. If not elevated at baseline, will not be monitored serially.
- 8 Studies at time of progression at the discretion of patients and treating physician if feasible (optional).
- 9 To be done every 12 weeks until relapse or progression (iCPD) for up to 2 years, for patients with CR/ICR, PR/iPR, SD/iSD response as defined in Section 8.0. For patients with iUPD, confirmatory scans must be performed at least 4 weeks, but no longer than 8 weeks, after iUPD was identified.
- 10 First tumor assessment should be performed 12 weeks ( $\pm$  1 week) following randomization. To ensure comparability, baseline scans and subsequent scans to assess response must be performed using identical technique (i.e. scans performed immediately following bolus contrast administration using a standard volume of contrast, the identical contrast agent, and preferably the same scanner). Maintain schedule every 12 weeks even if cycles are delayed.
- 11 Every three months thereafter to follow adverse events felt related until resolved to  $\leq$  Grade 2. Adverse Events to be evaluated using the NCI Common Terminology Criteria for Adverse Events (CTCAE v.5.0) (see Appendix V).
- 12 See Section 12.0 for details. Documentation of POLE or POLD1 mutation in tumor OR by cfDNA in plasma required prior to randomization. Please refer to Section 12.1.3 and the Correlative Studies Manual for details regarding collection.
- 13 To be done day 1 of each cycle (excluding cycle 1) for first 4 cycles.

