### 8.2 Response and Evaluation Endpoints

Response and progression will be evaluated in this study using the revised international criteria (1.1) proposed by the RECIST (Response Evaluation Criteria in Solid Tumors) committee as well as the Immune-Related modified RECIST. Investigators should continue treatment, as appropriate, in the absence of unacceptable toxicity, until unequivocal disease progression. This is particularly important for patients in whom pseudoprogression may have occurred. Follow up response assessments must be continued until unequivocal disease progression has occurred.

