#### 8.4 Response Duration (RECIST 1.1 and iRECIST)

Response duration will be measured from the time measurement criteria for CR/PR (whichever is first recorded) are first met until the first date that recurrent or progressive disease is objectively documented, taking as reference the smallest measurements recorded on study (including baseline).

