10.4 Follow-up Off Protocol Treatment

All patients will be seen at 4 weeks after completion of protocol therapy. Continued follow-up required for all patients every 3 months to collect information on ongoing toxicities, late toxicities (including second malignancies) and survival data. This follow-up will continue until death or conclusion of the trial.

PROTOCOL DATE: 2018-MAY-30

CRI-CCTG: 0001

CCTG: IND.235

For patients who go off protocol treatment with CR/ICR, PR/iPR, SD/iSD or iUPD ongoing, tumor assessments will be required every 3 months until relapse (see Section 5.0 for investigations to be performed). Please note for patients who go off protocol treatment with iUPD, confirmatory scans should be performed at least 4 weeks, but no longer 8 weeks, after iUPD was documented.

A Death report will be required on all patients. Due within 2 weeks of knowledge of death (see Appendix IV- Documentation for Study).

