### 13.2 Endpoints and Analysis

The primary endpoint is ORR by RECIST 1.1 in immunotherapy naïve patients with advanced solid tumors with detectable mutations as determined by central blood-based assay (cfDNA for POLE/D1 mutations). Patients with detectable mutations in tissue but with no detectable mutations based on plasma cfDNA will be excluded from this analysis.

Response rates will be reported using percentages over all randomized patients with 90% exact confidence intervals (CI) of each arm in a non-comparative analysis. In addition, exact logistic regression models will be used to assess the effect of treatment on objective response probability, adjusting for mutational load values and trial site.

Secondary endpoints include: ORR of nivolumab monotherapy and of nivolumab combined with ipilimumab in all treated patients. Response rates will be reported using percentages over all patients who have received at least one dose of treatment with 90% exact CI of each arm in a non-comparative analysis. In addition, exact logistic regression models will be used to assess the effect of treatment on objective response probability, adjusting for mutational load values and trial site.

Duration of response (DOR) will be calculated from time of response to documentation of progression or death or censored at last time of disease assessment among all patients who have responded. Kaplan-Meier method will be used to estimate median duration of response and 90% confidence interval in each arm.

The responses assessed by iRECIST will be analyzed similarly as that by RECIST 1.1.

To assess the safety and characterize toxicities of nivolumab combined with ipilimumab and nivolumab monotherapy in all patients, estimation of the adverse event profile associated with treatment will be performed. All toxicities regardless of attribution will be reported using the CTCAE version 5.0 criteria. Adverse events rates will be reported using percentages with 90% exact CI.

Correlation between detectable mutations in tumor and detectable mutations in blood will be assessed by Fischer's exact test in each arm.

Detectable mutations in the initial study population are *POLE*/*POLD1* mutations based on plasma cfDNA.

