PFS and OS of nivolumab monotherapy and of nivolumab combined with ipilimumab in patients with advanced solid tumors with detectable mutations as determined by plasma cfDNA, and in all treated patients (detectable mutations in tissue or cfDNA) will be evaluated as exploratory endpoints.

Kaplan-Meier method will be used to estimate probabilities of OS and PFS for each arm. Patients alive at the time of trial analysis will be censored as of the date of their last disease assessment. Medians and 90% CI will be provided, if available. No formal comparisons will be made between the two arms. Adjusted analyses will be also consider mutational load as one of the covariates.

Tumors will undergo whole exome and RNA sequencing to evaluate the genetic landscape of mutated tumors in responders versus non-responders to immune checkpoint blockade.

Detectable mutations in the initial study population are *POLE*/*POLD1* mutations based on plasma cfDNA.

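### Footnote 9 stops scheduled scans at an undefined 2 years while Section 8.2 sets no limit; if the cap is followed, Section 13.2 counts later deaths as DOR events but censors living responders

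*Combined protocol and SAP*

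**What the plan says.** All places are in the combined protocol and SAP.

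- **Section 5.0, footnote 9** (patients in CR, PR or SD): "To be done every 12 weeks until relapse or progression (iCPD) for up to 2 years". No start date is given. The footnote marks the row label, "Tumor Imaging (Chest, abdomen, and pelvis; other scans as necessary to document disease", and both post-treatment cells. The on-treatment cell instead carries footnote 10, which places the first scan 12 weeks after randomization, adds "Maintain schedule every 12 weeks even if cycles are delayed", and has no time limit. Section 5.0 opens by making its schedule mandatory for everyone entered.
- **Section 8.2:** "Follow up response assessments must be continued until unequivocal disease progression has occurred".
- **Section 10.4** (patients who stop treatment while in response, stable or with iUPD): "tumor assessments will be required every 3 months until relapse", with a reference to Section 5.0 for the investigations.
- **Sections 7.2 and 10.2:** treatment runs to progression with no maximum duration.
- **Section 13.2:** DOR runs from response to "documentation of progression or death or censored at last time of disease assessment" and is summarized by a Kaplan-Meier median with a 90% interval per arm. For PFS and OS: "Patients alive at the time of trial analysis will be censored as of the date of their last disease assessment".
- **Section 8.4:** response duration runs "until the first date that recurrent or progressive disease is objectively documented". Death is not named.
- **Sections 6.3 and 10.4:** follow-up continues until death or until the trial or its follow-up is closed.

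**The concern.** Sites hold two instructions on when to stop scanning a patient who is still responding, and scans not taken cannot be recovered. The choice also feeds into the analysis. Once scheduled imaging ends, a living responder leaves the DOR risk set at the last scan, while one who later dies stays in it until death and counts as an event. That is outcome-dependent censoring, and it acts only on the late part of the curve.

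DOR is a secondary objective. Section 2.3 cites preliminary data in MSI-H colorectal cancer with median DOR not reached in either cohort, so long responses are plausible, though the documents give no DOR for POLE or POLD1 tumors. A long median could then depend on which imaging rule a site followed. Exploratory PFS is exposed in the same way if deaths count as events.

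**Working it through.** The plan states no DOR figure, so there is none to reproduce.

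**1. Do the rules conflict?** Section 8.2 has no limit and no reference to Section 5.0, so the cap cannot be read into it. Section 10.4 has no limit of its own but refers to Section 5.0. That reference is to which investigations are done, not clearly to how long, yet a site could read the cap into it. Only Section 8.2 conflicts outright.

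**2. Does the cap apply on treatment?** The on-treatment cell cites uncapped footnote 10, footnote 9 marks the post-treatment cells, and treatment has no maximum duration. This favors an off-treatment cap. The mark on the row label leaves the other reading open.

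**3. Latest detectable progression if the clock starts at randomization.** Two years is 104 weeks, so the last 12-weekly scan is at 8 × 12 = 96 weeks. For a response first seen at week 12, the longest scan-detected duration is 96 − 12 = 84 weeks = 84 × 7 / 30.4375 = 19.3 months. For a response at week 24 it is 72 weeks = 16.6 months. One scan step is 84 / 30.4375 = 2.8 months.

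**4. Effect on the Kaplan-Meier median under Section 13.2.** Simulated responders.

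- From the documents: 12-week scans; 24-month accrual (uniform entry assumed); event at the scan that detects progression, or at death; living patients censored at the last scan.
- Assumed: exponential DOR; response first seen at week 12 (70%) or week 24 (30%); minimum follow-up 12, 24 or 36 months; exponential post-progression survival, median 6, 12 or 18 months; for the off-treatment clock, exponential time to stopping without progression, median 6, 12 or 24 months.

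Capped minus uncapped median, in months, as the range over scenarios:

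| True median | Clock from treatment stop | Clock from randomization, no later scans | Clock from randomization, half still scanned |
|---|---|---|---|
| 12–18 | 0 | −0.3 to 0 | −0.2 to 0 |
| 18.5–24 | −1.3 to +0.7 | −3.9 to +2.6 | −2.7 to +2.1 |
| 24.5–30 | −2.8 to +1.5 | −8.3 to +2.0 | −3.3 to +2.0 |
| 30.5–36 | −5.3 to 0 | −11.5 to −1.2 | −5.5 to 0 |

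Four scenarios in the last row, where even the uncapped median was not reached, are left out. At a true median of 24 the uncapped estimate is 24.8. The capped estimate is 24.8 with the off-treatment clock and 21.3 to 26.3 with the randomization clock. At a true 36 the uncapped estimate is 33.1 to 38.3 or not reached, against 30.4 to 35.9 (off treatment) and 22.9 to 30.6 (randomization).

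**5. Under Section 8.4 instead.** With death not an event, post-progression median 12 months and the randomization clock, estimates at true medians of 15, 16 and 17 do not change (16.6, 19.3, 19.3). At 18 and 24 they go from 22.1 and 27.6 to not reached.

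**6. Scale against sampling error.** Expected responders are 0.30 × 50 = 15 and 0.50 × 50 = 25. For n exponential times (n odd, no censoring), the sample median is order statistic (n+1)/2. Its quantiles are −(36/ln 2) × ln(1 − q), with q from a Beta((n+1)/2, (n+1)/2) distribution. The 5–95% range for a true 36 months is 19 to 63 (n = 15) and 22 to 56 (n = 25).

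**7. Censoring at the last scheduled scan (randomization clock).** The medians are 13.8, 16.6 and 19.3 at true 12, 15 and 18, and not reached at the tested values of 20, 22, 24 and 36.

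**The case against.** Section 5.0 makes its schedule mandatory, and Section 10.4 sends the reader there, so the cap can be defended as the operative rule. The Section 8.2 sentence closes a paragraph about treating through pseudoprogression and sets no scan interval. This stands in part: Section 10.4 is not a clear contradiction, but Section 8.2 still is.

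An off-treatment cap is the better-supported reading, and it does little: no change up to 18 months and about one scan step at most up to 30. The large differences need the randomization clock, long medians and no scan after the cap. The Table 1 note asks for progression to be documented after treatment stops, and Appendix IV has a Relapse/Progression Report, so some late progression would be captured. All of this stands.

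The cited long responses are preliminary and come from another tumor group. A median not reached in early data does not show one beyond 24 or 30 months. That stands too.

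A 2-year imaging limit is a legitimate choice about patient burden. That is so, but it needs a start date and an analysis rule that fits it.

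**Conclusion.** The conflict between footnote 9 and Section 8.2, the missing start point, and the differing treatment of death in Sections 8.4 and 13.2 can all be verified in the text. Following the cap together with Section 13.2 as written makes DOR censoring depend on outcome.

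The size rests on the assumptions in the working. It is essentially nil for true medians up to about 18 months. With an off-treatment cap it is at most about one scan step up to 30 months, and up to about 5 months too short at 30 to 36. With the cap from randomization and no later scans it goes either way near 24 months and reaches about 8 to 11 months too short at 30 to 36. All of this lies within the sampling variation of 15 or 25 responders.

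A reader might infer that median DOR is bound to be understated, that imaging certainly ends at 2 years even on treatment, or that the trial's main result is at risk. The documents support none of these. The direction is not fixed near 24 months, since it turns on data cutoff and post-progression survival, which are not given. The flowsheet points to an off-treatment cap. The primary ORR does not depend on scans after year 2. This is a minor secondary-endpoint issue, but small samples do not excuse a systematic distortion that wording can remove.

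**What to change.** Use one stopping rule for tumor imaging in footnote 9, Section 8.2 and Section 10.4.

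- **If the cap stays:** state when the 2 years begin and whether they apply on treatment; align Section 8.4 with Section 13.2 on death; and censor DOR and PFS at the last scheduled scan, so that deaths after scheduled imaging ends are not events. This costs only wording and analysis text. The downside is that long medians are reported as not reached (with the randomization clock, at tested true medians of 20 months or more).
- **If the cap goes:** delete the 2-year limit from footnote 9. The cost is continued 12-weekly scans. At a true median of 24 months and minimum follow-up of 24 months, the share of responders still in response when capped scans end is 12% to 31% with the off-treatment clock and 57% with the randomization clock. Of 15 + 25 = 40 expected responders that is about 5 to 12, or 23, plus patients with long-term SD. Whether that burden is justified is the sponsor's choice.
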